### 3.5.8 Analytic plan

All analyses will be according to the principle of intent-to-treat, i.e., analysis of site and individuals within the site as randomized. The primary individual-level outcomes are achieving three elements of the HCV treatment cascade (diagnosed, treated, achieving SVR). We have powered the study based on a comparison of the proportions among the three groups (see below). The denominator for all cascade indicators is the number of OAT patients who are screened positive for HCV and are enrolled in the study. The numerators, the number who completed the pre-treatment evaluation, started DAA treatment and achieved SVR, will be obtained from the electronic clinical data collection system. Data will be assessed for missingness. A repeated measures likelihood based mixed model with missing at random (MAR) assumptions will be used for the analysis of the primary outcome to compare the three allocations, adjusted for the stratification variables (geographic region) plus age and gender. We will also adjust for covariates that are predictive of missingness to be consistent with the MAR assumption. Sensitivity analyses as described below will be done to assess this assumption, which is a reasonable starting point given missing data is expected to be low. Results will be displayed as point estimates with corresponding 95% confidence limits. The primary (and secondary) outcomes will be tested at the 5% (2-sided) significance level.

Hypotheses

1) OAT facilities implementing the simplified integrated model will have adoption and penetration of HCV care elements, that will ultimately result in improved patient-level outcomes like HCV cure compared to standard of care (SOC);

2) Compared to No ECHO, clinicians at ECHO-facilitated sites will have improved HCV care cascade outcomes.

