In addition, we have planned to test for a linear trend among the intervention levels for the proposed outcomes, testing that SHIM+ECHO > SHIM with No ECHO > SOC. We also plan to test the treatment effects using similar methods for OAT dropout strata separately. In addition to direct effects, mediation and moderation regression will be conducted as described by Donaldson. Testing will be conducted at a Bonferroni corrected type I error level of 0.025 to control for multiple testing. Secondary and process outcomes will similarly be tested. These measures and their subscales will be compared as pre/post and over time using one-way ANOVA/Duncan test, with general linear models to identify differences in treatment effect stratified by the geographic region (cluster). Mean scores will be normalized, with comparisons between the three groups, with the referent being SOC. To address multiple testing, we will use the Benjamini-Hochberg method of controlling the false discovery rate. We do not expect missing data to be a concern since most of the data on primary outcomes will be derived from clinical source documentation; for the survey data, we expect that we will collect more than 90% of the data at the 24-week time point. We will, however, explore all patterns of missing data and compare those with and without data to determine whether the data may be MAR or not MAR (i.e. eliminate the missing completely at random assumption). We will conduct sensitivity analyses using an appropriate missing data method, such as multiple imputation.

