### 3.5.9 Power Analysis

We will need a sample size of 133 per group (total sample size of 399), to have 90% power at a 5% level of significance to detect a standardized effect size of 0.20 for a null hypothesis of no difference between the proportions in the three groups versus an alternative of at least one difference at the 24-week time point. Additionally, we will have 94% power with a 2.5% type I error rate (Bonferroni corrected) to detect a standardized effect size of 0.32 within each geographic strata. Conservatively, we expect a 10% loss of information at the 24-week time point. Therefore, we have inflated the sample size by 10% and will recruit a total of 480 patients for the Aim 3 outcomes.

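### The stated 90% power is for a three-group test of any difference; neither main hypothesis (SHIM versus SOC, ECHO versus no ECHO) has a stated power at this trial's size

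*Combined protocol and SAP*

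**What the plan says.** Section 3.5.9 (Power Analysis) asks for 133 patients per group, 399 in total, "to have 90% power at a 5% level of significance" and "to detect a standardized effect size of 0.20". The test is of a "null hypothesis of no difference between the proportions in the three groups versus an alternative of at least one difference". The total is raised to 480 (160 per arm) after allowing for a 10% loss of information. The section's only other power figure is 94%, for an effect size of 0.32 within each geographic stratum.

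Section 3.5.8 (Analytic plan) repeats the basis: "We have powered the study based on a comparison of the proportions among the three groups". It describes a mixed model that compares the three allocations. It then lists two hypotheses. The first is that clinics using SHIM do better than SOC. The second is "Compared to No ECHO, clinicians at ECHO-facilitated sites will have improved HCV care cascade outcomes". The Summary calls the same two the main hypotheses.

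Section 3.5.8 also plans a linear-trend test, "testing that SHIM+ECHO > SHIM with No ECHO > SOC", and gives two significance levels: "The primary (and secondary) outcomes will be tested at the 5% (2-sided) significance level", and later a Bonferroni level of 0.025.

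**The concern.** The quantity that was powered is not either question the trial sets out to answer. Rejecting equality of three arms does not say which arm differs. A reader will naturally take 90% as the chance of confirming each main hypothesis, and the plan gives no such figure.

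The second hypothesis is most exposed, because the ECHO comparison is what separates the two SHIM arms. A significant overall result could be reported as support for ECHO when SHIM alone produced it. A non-significant ECHO comparison could be read as no benefit although its power was never stated.

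**Working it through.** **Inputs from the documents.** 133 per group, effect size 0.20, 5% two-sided, 160 recruited per arm (3.5.9, 3.5.8, Aim 3). A 10% loss leaves 160 × 0.9 = 144. The Bonferroni level is 0.025 (3.5.8).

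**Assumptions, because the documents do not supply them.** 0.20 is Cohen's w over three groups; mean success is 50%; patients are treated as independent, since 3.5.9 mentions no clustering allowance.

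**1. The plan's own figure.** For a 2-df chi-square test the noncentrality is N·w² = 399 × 0.04 = 15.96. Power at 5% is 95.6%, not 90%; 90% would need about 317 patients in total. The printed 90% is matched by an unprinted alpha of 0.05/3 (90.0%), or by a two-group test with w = 0.20 at 133 per group (90.4%). So the meaning of 0.20 is not settled by the printed result.

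**2. Arm proportions giving w = 0.20.** With equal arms, w² = [mean of (pᵢ − p̄)²] / [p̄(1 − p̄)]. For equal spacing by e at p̄ = 0.5: (2/3)e²/0.25 = 0.04, so e = 0.1225. If one arm differs from two equal arms by δ: (2/9)δ²/0.25 = 0.04, so δ = 0.2121.

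**3. Power of SHIM+ECHO versus SHIM.** Power = Φ(|p₂ − p₁|/SE − z), with SE² = [p₁(1 − p₁) + p₂(1 − p₂)]/n and z = 1.960 (5%) or 2.241 (2.5%). For equal spacing at n = 133: SE = √[(0.250 + 0.235)/133] = 0.0604 and 0.1225/0.0604 = 2.03, so power is Φ(0.07) = 53% at 5% and Φ(−0.21) = 42% at 2.5%.

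| Pattern (SOC / SHIM / SHIM+ECHO, %) | 5%, n = 133 to 160 | 2.5%, n = 133 to 160 |
|---|---|---|
| Equal spacing (37.8 / 50.0 / 62.2) | 53-60% | 42-49% |
| SHIM gives three quarters of the gain (36.3 / 53.9 / 59.8) | 16-19% | 10-12% |
| ECHO gives all the gain (42.9 / 42.9 / 64.1) | 94-97% | 91-95% |
| SHIM gives all the gain (35.9 / 57.1 / 57.1) | no ECHO effect | no ECHO effect |

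All four patterns have the same w, so the three-group power at N = 399 is 95.6% in each. Pooling the variance under the null lowers the contrast figures by at most about one percentage point.

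**4. Other readings of 0.20.** As the pairwise standardized difference: 0.20 × √(133/2) = 1.63, giving 37% (5%) or 27% (2.5%); at 160 per arm, 43% or 33%. As w in a two-arm table, equivalent to a standardized difference of 0.40: 0.40 × √(133/2) = 3.26, giving 90% or 85% at 133 per arm.

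**5. SHIM versus SOC.** Under equal spacing at mean 50%, SHIM alone versus SOC has the same power as the ECHO contrast, by symmetry. Pooling both SHIM arms against SOC gives about 94% (5%) or 90% (2.5%) at 133 per arm. If all the gain comes from ECHO, the pooled contrast has only about 52% or 41%.

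**6. The trend test.** With three equal arms the linear contrast has weights (−1, 0, 1), which compares SHIM+ECHO with SOC. In the last row of the table (no ECHO effect) it has about 94% power at 133 per arm, 5% level.

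**7. Clustering.** The documents give no intracluster correlation. Assuming 0.01 to 0.05 with 40 patients per clinic, the design effect 1 + 39ρ is 1.39 to 2.95. On the standardized scale (difference 0.20 × √1.5 = 0.245, 160 per arm, 5%), equal-spacing power falls from 59% to between 46% and 25%, before any allowance for having only four clinics per arm.

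**The case against.** A reader might infer that the ECHO comparison has roughly 40-55% power. The documents do not support that as a flat statement. It requires 0.20 to be a three-group w and the arms to be equally spaced. Section 3.5.8 states an order of the arms; it gives neither spacing nor rates. The two-arm reading of w comes close to the printed 90% and would give the ECHO contrast about the same, although it conflicts with the three-group null that 3.5.9 describes.

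A reader might also infer that ECHO is always the weaker contrast. That fails: if the gain comes from ECHO, the pooled SHIM contrast is the weaker one. The ranking also depends on pooling, which the plan does not specify.

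Nor does 3.5.8 name a 2-df test as the decision rule. It describes a model comparing the allocations with confidence limits, and the 0.025 level is compatible with two tests. The contrasts are left unspecified rather than excluded.

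These points limit the number and do not close the gap. The trend test does not isolate ECHO, and neither do the comparisons referenced to SOC that 3.5.8 describes for the secondary and process measures. The claim of power above 0.95 in section 3.4.5 belongs to Aim 2 and assumes 900 patients with 200-300 per group, against 160 per arm here.

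**Conclusion.** The point stands on the text: power is stated for a three-group comparison, and for neither main hypothesis at this trial's size. A significant three-group or trend result can arise from SHIM alone and cannot establish an ECHO benefit.

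The size is conditional. On the three-group reading of 0.20, with mean 50% and independent patients, the ECHO contrast has anywhere from about 10% to 97% power, depending on how the gain divides between SHIM and ECHO and on the test level. Equal spacing, which is an illustration and not the plan's assumption, gives 42-60%. The pairwise reading gives 27-43%. Clustering lowers all of these. That one three-group figure is compatible with so wide a range is the reason the printed 90% says nothing about the second hypothesis.

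**What to change.** In 3.5.8, name two contrasts from the same mixed model as the primary tests: both SHIM arms pooled (stated explicitly) versus SOC, and SHIM+ECHO versus SHIM, each at the plan's Bonferroni level of 0.025. Label any three-group or trend test as supportive only.

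In 3.5.9, replace the single 90% with the power of each contrast under stated arm proportions, as a range over plausible patterns, and define the effect size. State that a non-significant ECHO contrast will not be read as evidence of no benefit; report its estimate and confidence interval.

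The cost is wording only, with no extra patients. The stated power for at least one hypothesis is likely to become less favourable.

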### 3.6 Premature Study Discontinuation

Participants may voluntarily withdraw from the study for any reason at any time. Site Coordinators may, with the approval of the PI, withdraw participants before their scheduled termination visit to protect their safety, and/or if participants are unable or unwilling to comply with study procedures. Participants also may be withdrawn if the study sponsors, government or regulatory authorities, or IRB terminate the study prior to its planned end date. Study staff will record the reason(s) for all withdrawals in participants' study records. If a participant chooses to withdraw, data collected from this participant will be deleted and will not be used for analysis. In all other cases, participant information will be used for analysis.

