### 3.5.7 Retention in the study

Given our intent-to-treat approach to outcome evaluation, discharge from the OAT program, non-completion of clinical assessment, non-initiation or non-completion of treatment will not result in withdrawal from the study. Collection of clinical data at OAT clinics does not require patient's presence, and this will not be affected by retention.

To ensure sufficient retention in follow-up assessments, we will use several strategies used in our studies of PWIDs in Ukraine where retention in all cases exceeds 83% at 12 months, including: 1) providing compensation time for travel time and assessment costs; 2) detailed locator information, including contact information of a chosen contact person, usually a relative or a social worker; 3) maintaining regular contact through visits to OAT clinics.

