### 4.2 Adverse Event (AE) Reporting

Adverse events (AE) are defined as any untoward medical occurrence experienced by participants during the study, and may or may not have a causal relationship with the treatment. Information regarding all AEs regardless of seriousness or severity will be recorded in the participant's source files. Grade 3 and higher adverse events and all creatinine AEs will be recorded on study forms. All SAEs must be reported on AE Log form. All AEs that result in a clinical hold or permanent discontinuation of study product are reported on AE Log form regardless of grade. Grade 3 and higher clinical AEs will be referred to a study clinician at the time of the visit.

All critical laboratory values will be reported as applicable per site SOPs. Participants who are not present at the study site at the time a laboratory AE requiring retesting or follow-up is identified will be followed as deemed clinically appropriate. With appropriate permission of the participant, and whenever possible, records from non-study medical providers related to untoward medical occurrences will be requested and required data elements will be recorded on study forms and/or in the participant's medical chart. All AEs regardless of severity will be followed clinically, until the AE resolves or stabilizes as per the appropriate toxicity algorithm. AEs will be assessed for all participants, regardless if they continue DAA or not, after enrollment through the final study visit.

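### Deleting the data of participants who choose to withdraw contradicts the intent-to-treat, all-enrolled analysis, and section 3.5.8 does not say when an absent cascade outcome is missing rather than not achieved

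*Combined protocol and SAP*

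**What the plan says.** On withdrawal, section 3.6 says: "If a participant chooses to withdraw, data collected from this participant will be deleted and will not be used for analysis". It then limits the rule: "In all other cases, participant information will be used for analysis". Section 3.5.7 narrows what counts as withdrawal: "discharge from the OAT program, non-completion of clinical assessment, non-initiation or non-completion of treatment will not result in withdrawal from the study". It adds that chart data can be collected without the patient being present.

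On the analysis population, section 3.5.8 says: "All analyses will be according to the principle of intent-to-treat, i.e., analysis of site and individuals within the site as randomized". It continues: "The denominator for all cascade indicators is the number of OAT patients who are screened positive for HCV and are enrolled in the study". Each numerator is the count of participants recorded in the clinical data system as having reached that step. Section 3.5.4 defines P3 as having an undetectable HCV RNA result 12 weeks after treatment completion.

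On missing data, section 3.5.8 says: "A repeated measures likelihood based mixed model with missing at random (MAR) assumptions will be used for the analysis of the primary outcome". It expects little missing data, plans to explore whether data are MAR, and plans sensitivity analyses, with multiple imputation as the only named method.

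On safety, section 4.2 says: "AEs will be assessed for all participants, regardless if they continue DAA or not, after enrollment through the final study visit".

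**The concern.** A participant decides to withdraw after the clinic's arm is fixed. Removing that person's records is therefore a post-allocation exclusion, which intent-to-treat is meant to prevent. The loss cannot be repaired: with the baseline record gone, the person is also absent from the mixed model, from the exploration of missingness and from any imputation. Section 3.6 exempts no safety data, so a participant who leaves because of a side effect could drop out of the adverse event tables.

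The second issue is one of definition. If the indicator is recorded achievement over all enrolled, an enrolled participant without an SVR12 result has not achieved P3. A MAR model instead treats that outcome as unknown and predicts it from participants who were tested. Non-testing is itself a cascade step (S1d in section 3.5.5), and section 3.2 says the project does not pay for laboratory testing, so dropping out before the test is part of what the trial measures. Section 3.5.8 does not say which absent records are missing and which are failures, so two analysts could follow the text and report different primary results.

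**Working it through.** **The provisions side by side.** Section 3.5.8 needs every enrolled participant in the denominator. Section 3.6 removes some of them. Both cannot be followed once anyone withdraws by choice. Section 3.5.7 gives no technical reason for the removal, since chart-based outcomes do not need the patient's presence.

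**The plan's own figure.** The documents give no withdrawal rate. The nearest figure is the 10% loss of information in section 3.5.9. At that loss 480 × 0.90 = 432 remain, above the 399 the section asks for. The issue here is bias, not numbers. The 10% is used below only as an illustration; it is not a forecast of withdrawal.

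**Effect of deletion.** Let w be the proportion withdrawing, and p_R and p_W the success rates among retained and withdrawn participants.

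- All-enrolled rate = (1 − w) × p_R + w × p_W
- Rate after deletion = p_R
- Bias = w × (p_R − p_W)
- If p_W = 0 and the all-enrolled rate is p, the rate after deletion is p / (1 − w)

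With 160 per arm (stated) and assumed success rates:

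- *Equal withdrawal of 10%, no successes among the withdrawn.* 112/160 = 70.0% becomes 112/144 = 77.8%; 48/160 = 30.0% becomes 48/144 = 33.3%. The difference goes from 40.0 to 44.4 points, or +4.4.
- *Equal withdrawal of 1% or 2%.* 40/0.99 = 40.4 and 40/0.98 = 40.8, or +0.4 to +0.8 points.
- *Ratio under equal withdrawal.* 77.8/33.3 = 70/30 = 2.33, unchanged. Equal proportional loss of this kind creates no effect where there is none.
- *Unequal withdrawal, true 50% in both arms.* 5% against 15% gives 0.50/0.95 = 52.6% and 0.50/0.85 = 58.8%, a spurious 6.2 points. Swapping the arms reverses the sign.
- *Opposite direction.* Suppose 16 of 160 withdraw after completing P1, and 72 of the 144 retained complete it. The all-enrolled rate is (72 + 16)/160 = 55%; after deletion it is 72/144 = 50%. Deletion lowers P1 by 5 points.

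**Effect of the MAR rule on P3.** Assume 40% of enrolled are treated, 80% of those are tested, and 95% of tests are undetectable.

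- Recorded achievement over all enrolled: 0.40 × 0.80 × 0.95 = 30.4%
- Treated but untested participants filled in at the tested rate: 0.40 × 0.95 = 38.0%

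The 7.6-point gap is the difference between two definitions of success, documented SVR12 and predicted cure. It does not by itself show that 38.0% is biased.

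**The case against.** The strongest reply is about scope. Only voluntary withdrawal triggers deletion; patients who never start treatment, do not complete it or leave OAT stay in. A reader might infer that the plan discards treatment failures in general; section 3.5.7 says otherwise. If few people withdraw, the effect is small. This stands and limits the size, but not the contradiction.

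A reader might also infer that both rules necessarily inflate success. The documents do not support that. Deletion inflates only if the withdrawn succeed less often than the retained. That is likely for SVR12, the last step, but P1 and P2 can be reached before withdrawal. The two rules can also pull the contrast in opposite directions: MAR raises P3 most where testing is lowest, and if that is standard of care (SOC), the difference narrows. Nor should one infer that MAR would push everyone untested towards the 95% cure rate; treatment status is observed, and a repeated-measures model can use it.

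On safety, sections 4.1, 4.2 and 4.4 provide for source-file records, SAE reports within three reporting days and roughly monthly review. Section 3.6 does not say that reports already filed are erased. What remains is that it exempts no safety data from deletion.

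Counting undocumented outcomes as failures has its own risk. Section 3.5.6 says SOC patients receive HCV care elsewhere, so some unrecorded outcomes there may be true successes. That objection stands and is taken up in the fix. Finally, the consent forms are not available for this review, so deletion may reflect a commitment made to participants.

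**Conclusion.** The contradiction between section 3.6 and section 3.5.8 is certain from the text. Followed as written, the plan produces a post-allocation exclusion that no later analysis can undo. It also sits uneasily with the adverse event coverage in section 4.2.

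The size is not known. It depends on how many withdraw, in which arms and at which step, and the documents give none of this. Under the assumptions above, the distortion ranges from under one point at 1-2% equal withdrawal to 4.4 points at 10%, or about 6 points in either direction if withdrawal differs by 5% against 15%.

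The MAR point holds in a narrower form: the model conflicts with the plan's own definition of the cascade indicators and with P3, and the rule separating missing from not achieved is absent. It does not follow that MAR estimates would be biased upwards. The planned sensitivity analyses do not settle it, because multiple imputation normally assumes MAR as well.

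**What to change.** In section 3.6:

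- Keep and analyse data collected up to withdrawal, and keep the participant in the intent-to-treat denominator.
- Continue chart-based collection of P1-P3 unless the participant revokes it.
- Delete research data only on explicit request, and report the number of such requests by arm.
- Retain safety reports already filed.

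In section 3.5.8:

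- State the primary rule: among enrolled participants with confirmed HCV RNA, a P1, P2 or P3 not documented after the external verification in section 3.5.6 counts as not achieved, in all arms. If the denominator is instead everyone enrolled, give the rule for RNA-negative participants, whom sections 3.5.3 and 3.5.6 exclude and who would otherwise be counted as failures.
- Make sure verification covers all three endpoints; the list in section 3.5.6 names diagnosis, not the completed pretreatment evaluation.
- Move the MAR model and multiple imputation to sensitivity analyses, and add a tipping-point analysis by arm.

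The cost is protocol and consent wording with IRB approval. The statistical downside is possible under-ascertainment in SOC, which could favour SHIM. The tipping-point analysis must address this by showing how many undocumented SOC outcomes would have to be successes to change the conclusion.
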